4.6 Blood Smears

Thick and thin blood smears will be collected for every enrolled child at baseline, day 14, and day 180 after treatment. The child's finger will be pricked with a lancet by a trained professional. We will use the smears to determine the child's malaria status. Additionally, we will record the child's core body temperature. If the child has a fever, we will administer a rapid diagnostic test. If the child is positive for malaria, we will give the child a referral to the health center. See chapter 8 for more on the blood protocol.

The RDT utilized depended on local availability. The brand used is described below: SD Bioline Malaria PF (PfHRPII) from November 19-28, 2019 for baseline (407 children) CareStart malaria PF (PfHRPII) from November 29-30, 2019 for baseline (43 children) Onsite (PfHRPII and pLDH) from December 3-16, 2019 for day 14 visits.

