6.1 Nasopharyngeal Swabs

Nasopharyngeal swabs will be collected from all study participants at 3 different time points (day 0, day 14, day 180).

The examiner will:

- 1. Place a pediatric flocked swab with a nylon tip through the right nostril and down the nasopharynx of each participant. Note that if the swab is not perpendicular to the frontal plane of the face, it is likely not in the inferior turbinate.
- 2. Once you reach the nasopharynx, rotate the swab 180° as you remove the swab from the nose.
- 3. Place the swab in a tube containing 1.0 mL DNA/RNA shield media by Zymo or STGG (skim milk, tryptone, glucose, and glycerin) media, cut the handle off using sterile scissors, and close the cap of the tube with the swab immersed.
- 4. The nasopharyngeal swab samples in STGG will initially be stored in the field at 4°C using an insulated storage bag with Fisher brand ice gel packs, and then transferred to -20°C. The nasopharyngeal swab samples in DNA/RNA shield media will be stored in ambient temperature in the field. Then transferred to a refrigerator or freezer.
- 5. The scissors used to cut calcium alginate swabs will be sterilized with alcohol pads or cleaned with bleach wipes between participants. When collecting specimens in DNA/RNA shield, scissors will be cleaned between participants first with bleach wipes, and then with alcohol pads.

Do not attempt to collect the NP swab if you are not successful after three attempts.

Nasopharyngeal swabs will be stored in DNA/RNA shield media by Zymo or STGG media, and standard microbiologic techniques will be used to isolate S. pneumoniae and test for resistance to erythromycin, tetracycline, sulfa-trimethoprine, oxicillin, and clindamycin. Resistant isolates will be assessed for the most common genetic resistant determinants (ermB and mefA) using a PCR-based assay. Serotype will be assessed using a nested PCR reaction for the most common serotypes, followed by the Quellung reaction for any untyped isolates.

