2.1 Planned Analyses

2.1.1 Longitudinal Trial

Four hundred fifty children between the ages of 8 days and 59 months may be enrolled in the trial and be offered placebo or azithromycin in a masked fashion. Relevant indicators will be collected using whole blood venipucture, nasopharyngeal swabs, fresh frozen stool, rectal swabs, and anthropometry measurements at days 0, 14, and 180. Children followed up within day 120 and day 240 will be included in primary day 180 analysis. Fifty randomly selected children (25 per arm) will have an additional rectal swab collected at days 2, 4, 6, 8, 10, 12 post-treatment.

Primary Analyses. Pairwise comparison of *Campylobacter*, *C. upsaliensis* and *C. hominis* using Fisher's exact test, corrected for multiple comparisons using Holm-Bonferroni method.

We will compare profile of *Campylobacter*, *C. upsaliensis* and *C. hominis* based on L_1 , L_2 distance, and PERMANOVA. We will compare diversity between arms at days 14 and 180 separately, using Shannon's Index and Simpson's Index.

Statistical considerations.

- Model adequacy will be checked by examination of residuals or other goodness of fit tests as needed. Inadequate model fit will prompt us to report alternative models.
- Multiple imputation will be used in case of missing baseline covariates (if applicable). Missing outcome variables will be handled by sensitivity analysis and reporting of conditional results.
- False Discovery Rate will be calculated for each estimated significant effect.

Secondary analyses.

Note that participants outside of WHO Child Growth Standards for WAZ (-6 to +5 SD), HAZ (-6 to +6 SD), or WHZ (-5 to +5 SD) will be excluded from all anthropometric analyses.

S. pneumoniae carriage and macrolide resistance Separate Fisher's exact test at days 14 and 180.

lytA occurence Separate Fisher's exact test at days 14 and 180.

erm B, mef A, pp2A Separate Fisher's exact test at days 14 and 180.

N. meningitides, H. influenzae, Moraxella, S. aureus Pairwise comparison of organisms using Fisher's exact test, corrected for multiple comparisons using Holm-Bonferroni method.

PERMANOVA of L_1 and L_2 distance of bacterial reads. Shannon's and Simpson's estimated gamma diversities will be compared by arm.

Malaria Fisher's exact test of parasitemia and clinical malaria at days 14 and 180.

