- weight gain Defined as grams per kilogram per day (g/kg/day) will be compared between arms separately at days 14 and 180 using linear regression. Baseline weight is accounted for in our metric of weight gain and will not be included in the regression analysis. We will use ordinary least squares method of estimatation and permutation tests to estimate coefficient p-values.
- HAZ, WAZ, WHZ, MUAC As secondary analysis, we will perform separate ANCOVA of anthropometric indicators at days 14 and 180, adjusting for baseline.

3 Sample Size Considerations

We assume a mean (standard deviation) alpha Shannon's index of 16.47 (7.12) using results from Thuy et al. [DAR⁺17]. Assuming 80% power and detectable effect size of 1.02 standard deviations and no loss to follow-up, we propose a sample size of 225 per group, totaling 450 study participants.

4 Randomization

The randomization will be conducted using R. The function sample with option replace=FALSE will be used to conduct the random shuffling. Note that the choice of the random number seed completely determines the randomization. To ensure the integrity of the randomization, we will use the procedure we used for MORDOR/Malawi.

Samples will be randomly grouped into 5-pools for processing, within an arm and a time point.

5 Abbreviations

ANCOVA Analysis of covariance

- $\mathbf{DSMC}\,$ Data and Safety Monitoring Committee
- ${\bf HAZ}$ height for age Z score
- MUAC Mid upper arm circumference
- ${\bf SAP}\,$ Statistical Analysis Plan
- \mathbf{WAZ} weight for age Z score
- \mathbf{WHZ} weight for height Z score

References

[DAR⁺17] T. Doan, A. M. Arzika, K. J. Ray, S. Y. Cotter, J. Kim, R. Maliki, and et al. Gut microbial diversity in antibiotic-naive children after systemic antibiotic exposure: A randomized controlled trial. *Clinical Infectious Disease*, 64, 2017.

6 Revision History

- 29 May 2019 Revised specification and wording of primary and secondary outcomes. Moved weight gain to secondary outcome. Clarified Bonferroni correction for certain species.
- 13 Jan 2020 Updated the pre-specified sample size for the sub-section of GAMIN sample (GAMIN QOD).
- 16 Jan 2020 Abbreviated the study name on title page.
- 20 Mar 2020 Added sample size considerations section and specification of day 180 time window.
- 08 May 2020 Specified WHO standard range for inclusion for anthropometric (child growth) analysis.
- 02 Jul 2020 Increased upper range of day 180 window from day 210 to day 240.

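### For malaria and pneumococcal outcomes measured child by child, the SAP plans only an unadjusted Fisher's exact test, leaving the collected day-0 status unused and giving no effect estimate

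*SAP*

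**What the plan says.** SAP 2.1.1, under secondary analyses, specifies "S. pneumoniae carriage and macrolide resistance Separate Fisher's exact test at days 14 and 180". The resistance genes and malaria follow the same pattern: "erm B, mef A, pp2A Separate Fisher's exact test at days 14 and 180" and "Fisher's exact test of parasitemia and clinical malaria at days 14 and 180". These entries contain no baseline term, stratification, effect estimate or confidence interval. The SAP sets no significance level for them; it mentions only a false discovery rate calculation.

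Day-0 samples are planned. Protocol 4.6 states "Thick and thin blood smears will be collected for every enrolled child at baseline, day 14, and day 180 after treatment". Protocol 6.1 states "Nasopharyngeal swabs will be collected from all study participants at 3 different time points", namely days 0, 14 and 180. The table in Protocol 4.11 schedules malaria smears and phenotypic pneumococcal resistance on all three days.

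The same SAP section treats growth differently. For HAZ, WAZ, WHZ and MUAC, "we will perform separate ANCOVA of anthropometric indicators at days 14 and 180, adjusting for baseline". Weight gain is analysed by linear regression with permutation p-values.

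SAP section 4 (Randomization) adds "Samples will be randomly grouped into 5-pools for processing, within an arm and a time point". It does not say which assays are pooled.

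**The concern.** A child who is parasitemic or colonized at day 0 may well be more likely to be so at day 14. If so, day-0 status explains part of the outcome variation, and a comparison that ignores it is noisier than it need be. Fisher's test on a 2x2 table takes no covariate, and its true type I error lies below the nominal level. Both features cost power.

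The missing estimate matters separately. If a malaria or carriage comparison is null, a p-value alone does not tell the reader whether an important effect has been excluded. The SAP gives no reason for adjusting growth outcomes for baseline but not these.

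**Working it through.** **Plan's own figure.** There is none to reproduce. SAP section 3 and Protocol 3.2 base sample size on diversity indices and give no rate, effect or power for carriage, resistance or malaria.

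**Inputs.**
- 225 per arm (SAP section 3). Taking off the Protocol's 15% loss (3.2) gives 225 × 0.85 = 191. The SAP itself assumes no loss, so 225 is also shown. Protocol 4.6 lists 407 + 43 = 450 baseline children, which agrees with 225 per arm.
- Assumed: two-sided 5%; rates of 60% v 47% and 30% v 19%; correlation phi between a child's day-0 and follow-up status of 0 to 0.59.

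**Step 1. Which outcomes have a day-0 value per child?**

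| Outcome | Usable day-0 value per child |
|---|---|
| Parasitemia, clinical malaria | Yes: one slide per child, and temperature at baseline |
| Pneumococcal carriage | Yes, if swabs are cultured individually |
| Carries a macrolide-resistant pneumococcus, yes/no | Yes, if cultured individually and all cultured children form the denominator |
| Resistance among isolates, including ermB/mefA on resistant isolates (Protocol 6.1) | No: undefined in non-carriers |
| Any assay run on pools of five | No: only a pool result exists |

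**Step 2. Fisher's true size.** Summing the null probabilities of all tables that the test rejects:

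| Common rate | 2% | 5% | 10% | 30% | 50% |
|---|---|---|---|---|---|
| 191 per arm | 1.6% | 2.8% | 3.3% | 3.9% | 3.6% |
| 225 per arm | 1.9% | 3.1% | 3.5% | 4.0% | 4.3% |

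**Step 3. Power at 191 per arm.** The Fisher and chi-square figures are exact. The stratified figures are for a Mantel-Haenszel test on day-0 status, from 20,000 simulated trials per cell. Day-0 prevalence was set to the higher of the two rates, and correlated statuses came from a bivariate normal.

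| Test | 60% v 47% | 30% v 19% |
|---|---|---|
| Fisher | 68% | 67% |
| Chi-square, unadjusted | 71% | 71% |
| Stratified, phi 0 | 72% | 71% |
| Stratified, phi 0.1 | 73% | 72% |
| Stratified, phi 0.19 | 74% | 72% |
| Stratified, phi 0.3 | 77% | 74% |
| Stratified, phi 0.4 | 79% | 78% |
| Stratified, phi 0.59 | 88% | 87% |

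The step from Fisher to the stratified test at phi 0 (about 4 points) is Fisher's conservatism. The gain from day-0 status is the rise from the phi 0 row: about 1 point at 0.1, 2 at 0.19, 4-5 at 0.3, 7 at 0.4 and 16 at 0.59. Under the null the stratified test's size was 4.7-5.2%.

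A separate simulation (1,500 trials per cell) used linear regression on arm and day-0 status with permutation p-values. For 60% v 47% it gave 76%, 80% and 88% at phi 0.19, 0.41 and 0.59, with size 4.7-5.3%.

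**Step 4. The same gain in children and in precision.** Adjustment multiplies the variance by about 1 − phi². The equivalent increase in sample size is 1/(1 − 0.19²) = 1.04, 1/(1 − 0.4²) = 1.19 and 1/(1 − 0.59²) = 1.53. For 60% v 47%, the unadjusted 95% half-width is 1.96 × √[(0.60×0.40 + 0.47×0.53)/191] = 9.9 points. At phi 0.4 it is 9.9 × √0.84 = 9.1 points.

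**Step 5. Dependence on n.** At 225 per arm Fisher's power is 77% and 74%. The stratified test gives 80% and 78% at phi 0, and 86% and 84% at phi 0.4. At the Protocol's 725 per arm less 15% (616), the normal approximation gives z = 0.13/0.0282 = 4.61 and 0.11/0.0243 = 4.53, so power exceeds 99% either way and the gain is in interval width only.

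**The case against.** A reader might infer that day-0 status exists for every child on every binary outcome, so that all the Fisher tests should be replaced. The documents do not support that. Random pooling in fives within arm and time point leaves no individual value at day 0 or follow-up for any pooled assay, and lytA, ermB, mefA and pp2A may be among them. Resistance measured on isolates is undefined in non-carriers. This objection stands and limits the point to the outcomes marked yes in the first table.

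A reader might also infer that Fisher's test gives up power for nothing in return. It does give something: it guarantees the type I error in sparse tables, which are plausible for clinical malaria, rare genes or pooled results. With 225/5 = 45 pools per arm, the unadjusted chi-square test's size reached 5.9% at a 10% rate. Fisher therefore keeps a role.

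The correlation is unknown, and there are reasons to expect it to be modest. Febrile children who test positive for malaria are referred (Protocol 4.6), and any resulting treatment would weaken the link to day 14. The SAP's day-180 analysis accepts visits from day 120 to day 240, so persistence may be slight. This also stands, and it is why the gain is shown from zero upward. It does not argue for leaving the baseline out: even at phi 0 the stratified test did no worse than Fisher.

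Finally, Fisher is unbiased by design here, and these are secondary outcomes that did not drive the sample size. That is correct; the point concerns efficiency and reporting.

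**Conclusion.** The point holds for slide-read parasitemia and clinical malaria. It holds for pneumococcal carriage, and for carrying a macrolide-resistant pneumococcus among all cultured children, if swabs are cultured individually. For these outcomes the planned test is valid but conservative, with a true size of about 1.6-4.3% across the rates examined. It leaves collected baseline information unused and is not paired with an estimate.

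Under the assumed rates at 191 per arm, Fisher's power is about 67-68%. Adjustment adds about 4 points by removing conservatism, plus between zero and about 16 points from day-0 status. The low end is plausible at day 180, and a larger gain is more plausible at day 14. All rates and correlations are assumptions. The missing effect estimate and interval do not depend on them.

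The documents do not show that the planned tests would give a wrong answer, only a less precise and less informative one.

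**What to change.** In SAP 2.1.1, for malaria and for pneumococcal outcomes confirmed as measured per child:

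1. Make the main analysis at each of days 14 and 180 a risk difference adjusted for the child's own day-0 status. Linear regression, standardized logistic regression or Mantel-Haenszel stratification would all serve; name one.
2. Report the 95% confidence interval, and take the p-value by permuting arm labels, as the SAP already does for weight gain.
3. Keep Fisher's exact test as a sensitivity analysis, and as the main test for sparse outcomes under a stated threshold.
4. Define macrolide resistance with all cultured children as denominator. If resistance among isolates is also reported, label it separately and leave it unadjusted.
5. List which assays are pooled, and analyse those with the pool as the unit.

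Missing day-0 values are already covered by the SAP's multiple imputation rule for baseline covariates.

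The cost is SAP wording, a change-log entry and a few lines of code, with no new data. The drawback is slightly more analysis work for little return where the day-0 correlation is weak. If unmasked results have already been seen, Fisher must remain the prespecified test and the adjusted analysis must be reported as unplanned, as the SAP introduction requires.

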3.3 Baseline Measurement

After enrollment and informed consent but prior to randomization, baseline samples will be collected. Children will undergo anthropometry (height, weight, mid-upper arm circumference), whole blood venipuncture, a finger prick for malaria blood smears, 2 NP swabs, a rectal swab and they will provide a fresh frozen stool. In addition, study staff will administer a baseline questionnaire inquiring about the child's age and sex as well as the mother's maternal age, education, number of children, and breastfeeding.

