MORDOR Project

October 20, 2021 Version 1.7

Statistical Analysis Plan

UCSF Francis I. Proctor Foundation Centre de Recherche en Santé de Nouna University of Heidelberg

Introduction

This document (Statistical Analysis Plan, SAP) describes the planned analysis and reporting for the clinical trial, **GAMIN: Gut and Azithromycin Mechanisms in Infants and Neonates in Burkina Faso**. It includes specifications for the statistical analyses and tables to be prepared for the interim and final Clinical Study Report. This study is a Phase IV clinical trial to compare methods to reduce childhood mortality using mass administration of azithromycin (Pfizer, CAS 83905-01-5) compared to placebo. The content of this Statistical Analysis Plan meets the requirements stated by the US Food and Drug Administration and conforms to the American Statistical Association's Ethical Guidelines.

The following documents were reviewed in preparation of this Statistical Analysis Plan:

- Azithromycin for the reduction of child and infant mortality: Longitudinal Component, Manual of Operations and Procedures
- Azithromycin for the prevention of neonatal mortality in Burkina Faso: an individualrandomized trial, Statistical Analysis Plan
- Statistical Analysis Plan, MORDOR Trial
- ICH Guidance on Statistical Principles for Clinical Trials

The planned analyses described in this SAP will be included in future manuscripts. Exploratory analyses not necessarily identified in this Statistical Analysis Plan may be performed to support the analysis. Unplanned analyses not delineated in this Statistical Analysis Plan will be documented as such in the final Clinical Study Report and manuscripts. Note that unplanned analyses will be broadly grouped into two categories:

- 1. Sensitivity analyses for pre-specified outcomes
- 2. Other unspecified analyses

Sensitivity analyses are defined as alternate ways of modeling the primary outcome to ensure the finding was not dependent on the analytic plan, and these will not be subject to a multiple comparisons correction. Other unspecified analyses will be declared hypothesis generating or subject to an alpha level of 0.001.

This document will be reviewed prior to the enrollment of patients. All subsequent changes will be indicated by detailed change log in the Appendix.

Contents

1	Summary	5
	1.1 Longitudinal Trial	5
2	Statistical Analysis	5
	2.1 Planned Analyses	5
	2.1.1 Longitudinal Trial	5
3	Sample Size Considerations	7
4	Randomization	7

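### The weight-gain regression leaves out baseline weight because g/kg/day is said to account for it, and names no age term; dividing by baseline weight does not do this, so precision is lost.

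*SAP*

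**What the plan says.** SAP 2.1.1, under secondary analyses, defines weight gain in g/kg/day. It "will be compared between arms separately at days 14 and 180 using linear regression", by ordinary least squares with permutation p-values. On covariates it states: "Baseline weight is accounted for in our metric of weight gain and will not be included in the regression analysis". No age term or other covariate is named.

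The next item treats HAZ, WAZ, WHZ and MUAC differently, by "separate ANCOVA of anthropometric indicators at days 14 and 180, adjusting for baseline".

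The population is "Four hundred fifty children between the ages of 8 days and 59 months". The same SAP section has a general fallback: "Inadequate model fit will prompt us to report alternative models". Protocol 3.3 describes a baseline questionnaire "inquiring about the child's age and sex", and weight is measured at baseline (Protocol 3.3 and 4.4).

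**The concern.** A per-kilogram rate is free of baseline weight only if gain is proportional to weight. Over the first five years of life it is not: a young infant gains several times as much per kilogram per day as a three-year-old. The outcome therefore still depends strongly on baseline weight and age, and in an arm-only regression all of that variation goes into the residual.

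The sentence rules out baseline weight. It does not rule out age, but does not prespecify it. Weight gain is also the growth measure that most needs adjustment, because unlike the z-scores it is not standardised for age.

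At stake is power for one secondary outcome. Growth is a stated objective with a directional hypothesis (Protocol 1.2, SAP 1.1), and neither document gives a power calculation for it. A null result from a needlessly noisy model could be misread as no effect on growth.

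**Working it through.** The plan gives no SD, effect size or power for weight gain, so there is no figure of its own to reproduce.

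**1. Does dividing by baseline weight remove the dependence?** Assume an illustrative weight curve: 3.3 kg at birth, 7.6 at 6 months, 9.3 at 12, 11.8 at 24 and 18 at 60, linear between points. Six-month gain in g/kg/day, over 180 days:
- from birth: 4,300 / 3.3 / 180 = 7.2
- from 6 months: 1,700 / 7.6 / 180 = 1.2
- from 12 months: 1,250 / 9.3 / 180 = 0.75
- from 24 months: (6,200 / 6) / 11.8 / 180 = 0.49

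The rate falls about fifteen-fold across the eligible ages. A separate simulation with a different assumed curve (about 3.7 kg at 8 days, 10.4 at 12 months, 18 at 59 months) gave correlations of g/kg/day with baseline weight of -0.60 to -0.65 at day 180 and -0.31 to -0.57 at day 14.

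**2. What does leaving the covariates out cost?** With randomised arms, adjusted SE ≈ unadjusted SE × √(1 − R²), where R² is the share of outcome variance explained by the covariates.

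From the documents: n = 450 in two equal arms, ages 8 days to 59 months, day-180 window of 120 to 240 days (SAP 2.1.1). Assumed: the first curve above, 12% between-child variation in weight, and residual SD of 0.2, 0.5 or 1.0 g/kg/day at day 180 and 1, 2 or 4 at day 14. Uniform ages put (6 − 0.27) / (59 − 0.27) = 10% of children under 6 months. Flexible age means age, log-age and squared log-age. Each cell gives results for the three residual SDs in order.

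| Visit, share under 6 months | R², weight | SE ratio | R², weight + flexible age | SE ratio |
|---|---|---|---|---|
| Day 180, 10% | 0.42 / 0.33 / 0.19 | 0.76 / 0.82 / 0.90 | 0.93 / 0.73 / 0.42 | 0.26 / 0.52 / 0.76 |
| Day 180, 5% | 0.35 / 0.23 / 0.11 | 0.81 / 0.88 / 0.94 | 0.89 / 0.60 / 0.29 | 0.33 / 0.63 / 0.84 |
| Day 180, none | 0.32 / 0.09 / 0.02 | 0.82 / 0.95 / 0.99 | 0.50 / 0.14 / 0.04 | 0.71 / 0.93 / 0.98 |
| Day 14, 10% | 0.27 / 0.13 / 0.04 | 0.85 / 0.93 / 0.98 | 0.59 / 0.28 / 0.09 | 0.64 / 0.85 / 0.95 |
| Day 14, none | 0.04 / 0.01 / 0.00 | 0.98 / 0.99 / 1.00 | 0.06 / 0.02 / 0.00 | 0.97 / 0.99 / 1.00 |

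Example for the middle case (5% under 6 months, SD 0.5): √(1 − 0.23) = 0.88 with weight and √(1 − 0.60) = 0.63 with weight and age. In sample-size terms, 225 × 0.77 = 173 or 225 × 0.40 = 90 children per arm, analysed with adjustment, would match 225 without it.

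A lighter assumed curve (3.0, 6.8, 8.2, 10.4 and 15.8 kg at the same ages) changes R² by 0.04 or less. The SE ratios are the same at n = 1,450, so the protocol's 725 per arm does not alter the result. In the separate simulation a linear age term added almost nothing beyond baseline weight over the full age range; the relation is curved, so the age term must be flexible.

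**3. Detectable difference, day 180, 10% under 6 months.** (1.96 + 0.84) × √(2/225) = 0.264 total SDs (two-sided 5% and 80% power assumed). Over the three residual SDs this is 0.24-0.35 g/kg/day unadjusted, 0.18-0.31 with baseline weight and 0.06-0.27 with weight and age.

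**4. Validity.** With no treatment effect, over 5,000 simulated trials, the permutation test rejected at 0.049 unadjusted and 0.055 adjusted (simulation error 0.003). Both agree with 0.05 within two simulation errors. The unadjusted estimate was unbiased in every setting.

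**The case against.** The strongest reply is that this is an efficiency preference and not an error. The contrast is unbiased, the test is valid, the outcome is secondary, and the plan claims no power for it. That stands, and it limits the point to precision.

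It can also be said that baseline-adjusted WAZ already gives an age-standardised analysis of the same weights. That softens the practical loss, but WAZ is a different outcome and leaves the weight-gain analysis as it is.

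Two provisions in the SAP might seem to help. The model-fit clause applies only after poor fit and names no covariate, and an arm-only regression reproduces both arm means exactly, so residual checks need not reveal the omission. The sensitivity-analysis category in the SAP Introduction is defined for the primary outcome.

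On size, the largest reductions come from the flexible age term, which the sentence does not forbid; the sentence itself accounts only for the baseline-weight part. The range is wide because the age mix is unknown. The trial's name, "Gut and Azithromycin Mechanisms in Infants and Neonates in Burkina Faso", and the home visits for children under 28 days (Protocol 4.2) make a sample without young infants unlikely, but neither is an age distribution. If all children were at least 24 months old, baseline weight would gain almost nothing (SE ratio 0.98-1.00 at day 180).

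The timing objection also has force. The 450 children with baseline dates of 19-30 November 2019 (Protocol 4.6) reached day 240 by late July 2020, over a year before this SAP version of October 2021.

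**Conclusion.** The concern holds. The stated reason for leaving out baseline weight is wrong for this age range, and nothing else in the plan supplies the adjustment. The consequence is lost precision in one secondary analysis, without bias or inflation of the type I error.

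Under the assumptions above, the exclusion of baseline weight alone forgoes a day-180 SE reduction of 10-24% with uniform ages, 6-19% with 5% under 6 months and 1-18% with none. With flexible age added, the reductions are 24-74%, 16-67% and 2-29%. At day 14 with uniform ages they are 2-15% for weight and 5-36% for weight and age; with no child under 6 months they are at most 3%. The upper ends need low residual noise and should not be taken as expected values. Confidence is high on direction and medium on size, because the growth curve, residual SD and age mix are all assumed.

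**What to change.** Delete the sentence that excludes baseline weight. Prespecify weight gain at days 14 and 180 regressed on arm, baseline weight, flexible baseline age (a spline or log-age terms) and sex. Keep OLS, and obtain the permutation p-value for the arm coefficient by permuting arm labels and refitting. Report the currently specified unadjusted model alongside. The gain from sex was not quantified; it is included as a routine baseline covariate already collected.

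The cost is one sentence in the SAP and no new data. The drawback is timing. The change must be entered in the change log before any unmasked growth analysis. If that analysis has already been done, the unadjusted model should remain the prespecified one and the adjusted model be labelled post hoc.
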